### 7.4.2 *Nutritional advice and education*

#### 7.4.2.1 *Nutritional advice and education*

Participants will receive nutritional advice based on the food intake they log into their food diary [24]. Users will be educated on what they eat and get advice on how to improve their intake to meet their requirements. Educating the user on their food intake is important to ensure an improved eating pattern in the future. Therefore, the nutritional advice will be given in short passages of text, these feedback passages are derived from the nutritional database of VitalinQ and provide information as to whether the intake of a specific nutrient is high, low or as required and (if necessary) how to improve that intake and in most cases why.

[figure not shown]
## 8 My-AHA User Platform interface

The My-AHA platform is a web-based interface that has been designed for use via computer, tablet PC, and/or smart mobile telephone.

The platform interface covers the following areas:

1. Language selection (multi-language platform)
2. User login (password secured)
3. Menu interface enabling access to the User Dashboard, under which the user can select from 3 different options
  - a. Goals
  - b. Interventions
  - c. Results
4. An a risk analysis page, which enables the user to identify their current level of risk for diseases such as dementia. The risk analysis page also enables the user to model the effect of changing different modifiable risk factors (e.g. increasing their level of exercise) and how these lifestyle changes result in measureable change to their risk of chronic diseases in the future. This provides the user with both a simple informational tool that also provides motivation to undertake a change to lifestyle which decreases risk for disease.

The purpose built My-AHA Platform is illustrated in the Figures below.

**Dashboard ([name]):**

- Profile: [name]
- Email: [contact]
- Menu items: My Dashboard, Risk Assessment, My-AHA Apps, My Personal Information, Activities around the world, Available interventions, Log Out.

**Cognitive Training - Goals:**

No apps are connected to My-AHA. Select and connect your first app to start setting your goals.

- ISMB COGNITIVE PLATFORM #Cognitive training
- ISTOPPFALLS #Falls #Physical activity
- VITALINO #Physical activity #Nutrition
- ORIGINAL PLATFORM #Social life
- ORIGINAL PLATFORM #Social life

**Cognitive Training - Interventions:**

Look at the interventions for this activity domain. You can add them to your plan and customize them.

- WORKING MEMORY N-Back Training
- VISUAL SPATIAL TRAINING Few words explaining
- OTHER COGNITIVE TRAINING Improve your attention....
- OTHER COGNITIVE TRAINING Improve your orientation....

**Cognitive Training - Visual Spatial Training:**

**Frequency:** 1 Session, 3 times per week (equally spaced; e.g. Monday, Thursday, Saturday).

**How does it work?** n-back training works in conjunction with visual spatial n-back training; hence, alternating on a bi-weekly basis between n-back training and visual spatial n-back training. Example: Week 1: 3 session n-back training, Week 2: 3 session visual spatial n-back training, Week 3: 3 session n-back training, Week 4: 3 session visual spatial n-back training.

**Session duration:** 20 minutes

**Observations:** -

**ADD TO MY INTERVENTION**

**RESULTS:** Look at your progresses!

**Frequency:** Monitor activities you've done per week.

**RESULTS:** Look at your progresses!

**Frequency:** Monitor activities you've done per week.

**RESULTS:** Look at your progresses!

**Frequency:** Monitor activities you've done per week.

## 9 Safety and Screening Assessments

### 9.1 Adverse Events

The Principal Investigator or site staff are responsible for detecting, documenting, and reporting events that meet the definition of an Adverse Event (AE) or Serious Adverse Event (SAE).

#### 9.1.1 *Definition of Adverse Events (AE)*

An AE is any untoward medical occurrence associated with the use of an intervention in humans, whether or not considered intervention-related. Therefore an AE can be ANY unfavorable and unintended sign, symptom, or disease temporally associated with the use of a product, without any judgment about causality.

Events meeting the definition of an AE **include**:

- Exacerbation of a chronic or intermittent pre-existing condition including either an increase in frequency and/or intensity of the condition.
- New conditions detected or diagnosed after product administration even though it may have been present prior to the start of the study.
- Signs, symptoms, or the clinical sequelae of a suspected intervention interaction.
- Clinically significant abnormal findings should be recorded as AEs. A “clinically significant” finding is one that affects clinical management, including additional visits, monitoring or referrals, diagnostic tests, or alteration of treatment, or that is considered clinically significant by the investigator. A clinically significant finding may be a change in a test that has previously been abnormal but now requires additional action.

Events that **do not** meet the definition of an AE include:

- Anticipated day-to-day fluctuations or expected progression of pre-existing disease(s) or condition(s) present or detected at the start of the study unless judged by investigator to be more severe than expected for the participant’s underlying condition.
- Abnormal clinical measurements that are not labelled clinically significant (see definition above).
- Situations where an untoward medical occurrence did not occur (social and/or convenience admission to a hospital).
- Overuse of the intervention in the absence of other AEs will not be reported as an AE in its own right.
- Adverse events are recorded from the time that informed consent is signed.

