## 7 My-AHA Interventions

The intervention in this study is defined as the My-AHA platform. Participants randomized into the intervention arm will have access to the full My-AHA intervention platform (see also Section 8 My-AHA User Platform interface). Participants in the control group will not have access to the intervention package (no treatment control). All participants recruited into the study have no active disease state being treated. All participants meet study criteria for pre-frail status, a non-clinical disease state.

The protocol in the intervention arm is designed to prevent deterioration from a non-clinical state (pre-frail) into the disease state (frail).

The no-intervention control arm will not receive any element of the My-AHA intervention, a no-intervention non-disease control group. Participants in both study arms undergo formal assessment of clinical frailty status at 4 timepoints (baseline, 6 mo, 12 mo, 18mo). **Development of clinical frailty is considered an adverse endpoint for the participant in this study.**

Where a control group participant displays evidence of clinical decline at 6 or 12mo assessment points (defined as meeting clinical criteria for frailty) they will be offered access to the My-AHA intervention suite. We cannot estimate or predict what proportion of the control participants may develop frailty during the 18 month trial as there is no published data on incidence, age-dependent prevalence, or on average rate of decline into frailty from pre-frail states.

Participants randomly allocated to the intervention group will be provided with access to tailored intervention packages. Intervention packages will target domains of pre-frailty (e.g. physical, social, cognitive, nutrition) identified at baseline assessment for each participant. The intervention packages will be revised following each assessment point to accommodate for changes in domain specific areas of pre-frailty.

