**IMPORTANT NOTE:** For participants in the control group access to interventions will not be provided – this is a no-treatment control group. **The exception is when a control participant is found to meet clinical criteria for physical frailty at any of the post-baseline assessment points (6 month or 12 month). If progression to physical frailty is detected in a control group participant, that participant will be provided with immediate fully supported access to the physical intervention package to meet ethical obligations to the participant.**

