### 7.1.2 *Fitness and Mobility Exercise program (FAME)*

FAME is a standardised group-based exercise programme which participants will complete one session per week under the supervision of a physical exercise instructor (appropriately qualified and trained fitness instructors, physical therapists or occupational therapists). Each group session will be undertaken with a ratio of no greater than 1 instructor per 5 participants.

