### **9.1.3 *Time Period and Frequency for Collecting Adverse Event and Serious Adverse Event Information***

Collection of AEs and SAEs will begin at the time a participant signs informed consent and continues until the follow-up contact.

All SAEs will be recorded and reported to Project Management Board (PMB) within 24 hours of the investigator becoming aware of the SAE.

Investigators are not obligated to actively seek AEs or SAEs in former study participants. However, if the investigator learns of any SAE, including a death, at any time after a participant has been discharged from the study, and he/she considers the event reasonably related to the intervention or study participation, the investigator must promptly notify the PMB.

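### The adverse event definition depends on use of the intervention, so it does not fit the no-treatment arm or the time before first use, and it conflicts with collection from consent

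*Protocol*

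**What the plan says.** The Protocol's safety section defines an adverse event in two sentences, both referring to exposure. Section 9.1.1 opens: "An AE is any untoward medical occurrence associated with the use of an intervention in humans, whether or not considered intervention-related". It then describes any unfavourable "sign, symptom, or disease temporally associated with the use of a product, without any judgment about causality". Neither sentence asks for a causal link, but both presuppose that something has been used.

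Four bullets list what is included. One, for new conditions, also refers to exposure: "New conditions detected or diagnosed after product administration even though it may have been present prior to the start of the study". Another concerns suspected interactions with the intervention. The other two have no exposure wording: worsening of a pre-existing condition, and abnormal findings ("Clinically significant abnormal findings should be recorded as AEs").

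Section 7 sets the exposure of the control arm: "The no-intervention control arm will not receive any element of the My-AHA intervention". The exception is a control found physically frail at the 6 or 12 month assessment; "that participant will be provided with immediate fully supported access to the physical intervention package".

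The collection rule does not depend on exposure. Section 9.1.3 says: "Collection of AEs and SAEs will begin at the time a participant signs informed consent". Section 9.1.1 has a bullet to the same effect, but it stands in the list of events that do not meet the definition.

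**The concern.** In a trial with an untreated arm, the control events are the background against which harm from the intervention is judged. The intervention here includes exercise in pre-frail adults aged 60 and over, so some events will occur whether or not the programme causes them. If staff apply a definition that presupposes use, they have grounds to leave a control's event off the adverse event record and to enter the same event for an intervention participant. The arms would then differ in what is counted as well as in what happened. An excess in the intervention arm could come from the wording alone, and a real excess could be explained away by it. Control events that were never recorded cannot be recovered at the analysis stage.

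Contact may add to this. Section 9.1.5 asks about problems since the last visit or contact. Under section 7.1.2, intervention "participants will complete one session per week under the supervision of a physical exercise instructor", whereas Table 6 schedules controls only at 6, 12 and 18 months after baseline. Nothing in section 9.1 says how events that surface at intervention contacts are to be distinguished from those found at assessments.

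**Working it through.** The protocol gives no figure for adverse event rates, so the check is mainly a comparison of its provisions.

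**1. Which text decides what is recorded?** Section 9.1 makes the investigator and site staff responsible for events that meet the adverse event or serious adverse event definition. Section 9.1.3 says when collection runs. It does not say what counts. The definition in 9.1.1 is therefore the gate.

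**2. Who fits the definition, read literally?**

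| Participant and period | Intervention used? | Fits the two defining sentences? | Within the 9.1.3 collection window? |
|---|---|---|---|
| Intervention arm, consent to first use | No | No | Yes |
| Intervention arm, after first use | Yes | Yes | Yes |
| Control, no access given | No | No | Yes |
| Control found frail, after access | Yes | Yes | Yes |

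The first and third rows are the contradiction: events fall inside the collection window but outside the definition. The fourth row shows a selection effect. The only controls who fit the defining sentences are those already found frail, and only after they have received the intervention.

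**3. How many participants, and for how long?** Section 4 allocates 25 to control and 25 to intervention.

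- Control share: 25 / 50 = 50%. This is an upper limit for participants who never use the intervention, because some controls may be given access.
- Section 7 states that the proportion of controls becoming frail cannot be estimated, so never-exposed controls could number anywhere from 0 to 25.
- Access can be given no earlier than the 6 month assessment. Every control is therefore unexposed for at least 6 of 18 months: 6 / 18 = one third of follow-up. For a control given access at 12 months it is 12 / 18 = two thirds. For one never given access it is all of it.

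**4. What else in the protocol captures control events?**

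- *Serious events.* Section 9.1.2 lists outcomes such as death and inpatient hospitalization without an exposure condition. Section 9.1.7 requires all new serious events to be reported whatever their relationship to study procedures. However, its minimum report asks for the period of product intake, which an unexposed control does not have.
- *Falls and diagnoses.* Section 6.4.2 and Appendix 6 ask every participant at 6, 12 and 18 months about falls since the last assessment (with a description), and about diagnoses and medication. These answers do not carry the severity and outcome assessment of section 9.1.4 or the follow-up of section 9.1.6.
- *Other non-serious events.* Only the two exposure-free bullets in 9.1.1 help, and they are examples placed under a definition that presupposes use.

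**5. Result.** The exposed gap is non-serious events in controls and, in both arms, before first use. How many would go unrecorded depends on how staff resolve the contradiction, and the protocol gives nothing from which to calculate that.

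**The case against.** The strongest reply is that 9.1.1 should be read whole. The same section says that events are recorded from the signing of consent, which precedes any use. Section 9.1.3 refers to any consenting participant, not to one arm, and the questions in 9.1.5 are not restricted by arm. Two inclusion bullets need no exposure. A sensible investigator would record a control's event, and serious events, falls and new diagnoses have the other routes described above. How the arms are compared is commonly left to the statistical analysis plan.

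Much of this stands, and it rules out two stronger readings. A reader might infer that no control can have an adverse event, so that the arms cannot be compared for safety at all. The documents do not support that: frail controls gain access, collection from consent covers both arms, and the serious-event rule and the follow-up questionnaire apply to controls too. A reader might also infer that the weekly group sessions give the intervention arm a known, much larger number of occasions for reporting events. The protocol nowhere says that adverse event questions are asked at those sessions. It assigns detection to the investigator and site staff, and describes the session leaders as exercise instructors. Unequal contact is plausible, but its effect is not established.

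What the reply does not remove is the contradiction. A rule on timing does not change what counts as an event, and the consent line that would help stands among the things that do not meet the definition. Relying on each site to disregard the definition's wording is not a safeguard. The definition itself belongs to the protocol and governs recording before any analysis plan applies.

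**Conclusion.** The point holds as an internal contradiction with a plausible safety-reporting bias. The definition in 9.1.1 does not fit controls who have not used the intervention (up to 25 of 50 for the whole trial, and all 25 for at least the first 6 of 18 months), nor either arm between consent and first use. It conflicts with collection from consent in 9.1.3 and with the misplaced line in 9.1.1 itself. The likely consequence is under-recording of non-serious events in controls, which would make the intervention look less safe than it is and leave a real excess open to dispute.

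The conclusion assumes that staff apply the definition as section 9.1 directs. If they record every control event regardless, the bias from the definition disappears. Its direction is predictable, but its size cannot be derived from the protocol. The between-arm comparison is compromised, not impossible.

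**What to change.** Five changes, all in section 9.1 and the adverse event form:

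1. In 9.1.1, define an adverse event as any untoward medical occurrence in a participant of either arm from informed consent, whether or not the intervention has been used.
2. In the bullet on new conditions, make informed consent the reference point in place of administration of a product.
3. Move the consent-timing bullet out of the list of events that do not meet the definition.
4. In 9.1.5, require the questions to be asked in both arms at the existing 6, 12 and 18 month assessments, covering the whole interval since the previous assessment.
5. Record whether each event was first detected at a scheduled assessment or at an intervention contact, so that the arms are compared on events elicited at scheduled assessments and the rest are listed separately.

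The cost is a few lines of protocol text, one field on the form, and slightly more adverse event recording in controls. No visits are added.

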### **9.1.2 *Definition of Serious Adverse Event (SAE)***

An SAE is considered serious if, in the view of either investigator or medical supervisor, it results in any of the following outcomes:

- Death,
- A life-threatening AE (an AE is considered “life-threatening” if, in the view of either the investigator or medical supervisor, its occurrence places the participant at immediate risk of death. It does not include an AE that, had it occurred in a more severe form, might have caused death. The determination of whether an AE is life-threatening can be based on the opinion of either the investigator or medical supervisor. Thus, if either believes that it meets the definition of life-threatening, it must be considered life-threatening for reporting purposes).
- Inpatient hospitalization,
- A persistent or significant incapacity or substantial disruption of the ability to conduct normal life functions, or
- Important medical events that may not result in death, be life-threatening-, or require hospitalization may be considered serious when, based upon appropriate medical judgment, they may jeopardize the participant and may require medical or surgical intervention to prevent one of the outcomes listed in this definition. Examples of such medical events include allergic bronchospasm requiring intensive treatment in an emergency room or at home, blood dyscrasias or convulsions that do not result in inpatient hospitalization, or a fall requiring hospitalisation.

This definition of an SAE permits either the medical supervisor or the investigator to decide if an event is serious. Because SAEs are critically important for the identification of significant safety problems. For example, the investigator’s perspective may be informed by having actually observed the event, and the medical supervisor is likely to have broader knowledge of the intervention and its effects to inform its evaluation of the significance of the event. If either the medical supervisor or investigator believes that the event is serious, the event must be considered serious and evaluated by the sponsor for possible expedited reporting.

### **9.1.3 *Time Period and Frequency for Collecting Adverse Event and Serious Adverse Event Information***

Collection of AEs and SAEs will begin at the time a participant signs informed consent and continues until the follow-up contact.

All SAEs will be recorded and reported to Project Management Board (PMB) within 24 hours of the investigator becoming aware of the SAE.

Investigators are not obligated to actively seek AEs or SAEs in former study participants. However, if the investigator learns of any SAE, including a death, at any time after a participant has been discharged from the study, and he/she considers the event reasonably related to the intervention or study participation, the investigator must promptly notify the PMB.

#### **9.1.4 Assessment of Adverse Events**

The severity of each AE will be assessed by the investigator, or designee approved and documented for this study, as mild, moderate, or severe based on the below definitions:

- **Mild:** Event that is usually transient and may require only minimal treatment or therapeutic intervention. The event does not generally interfere with usual activities of daily living
- **Moderate:** Event that is usually alleviated with additional specific therapeutic intervention. The event interferes with usual activities of daily living, causing discomfort, but poses no significant or permanent risk of harm to the participant.
- **Severe:** Event that interrupts usual activities of daily living or significantly affects clinical status, or may require intensive therapeutic intervention.

Note that severity is not the same as “seriousness”. Outcome will be assessed using the following categories: recovered/resolved, not recovered/not resolved, recovered/resolved with sequelae, fatal, or unknown.

#### **9.1.5 Method of Detecting Adverse Events and Serious Adverse Events**

Care will be taken not to introduce bias when detecting AEs and/or SAEs. Open-ended and non-leading verbal questioning is the preferred method to inquire about AE occurrence. Appropriate questions include:

- “How are you feeling?”
- “Have you had any (other) medical problems since your last visit/contact?”
- “Have you taken any new medicines, other than those provided in this study, since your last visit/contact?”

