### 7.1.1 *Otago home-based exercise program (OEP)*

The OEP will be deployed as a home-based exercise programme used by older adults in their own homes without expert's supervision. Prior to commencing the OEP program each participant will have a home visit from an exercise instructor who will prescribe an individually tailored set of exercises according to the participant's clinical history and fitness level. The instructor will also provide each participant with detailed instructions regarding the correct implementation of each exercise. Participants will be provided with a booklet listing the exercises including short description and repetitions for each set as well as adjustable ankle cuff weights, which must be easy to take on and off. For participants, unable to exercise from a standing position, a chair-based exercise programme will be provided resistance-based training using ankle weights being replaced with resistance-bands.

Participants will undertake the OEP program one session per week, as each participant will engage in one additional group-based exercise session that targets the same domains as in the OEP. In addition, the OEP advice of undertaking a walking activity will be replaced with a recommendation of undertaking some form of endurance training for one additional session per week. This modified OEP program, including group exercise and endurance training, will result in a total of 3 hours of physical training per week.

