#### **9.1.6 Follow-up of Adverse Events and Serious Adverse Events**

After the initial AE/SAE report, the investigator is required to proactively follow each participant at subsequent visits/contacts. All AEs and SAEs will be followed until resolution, until the condition stabilizes, until the event is otherwise explained, or until the participant is lost to follow-up.

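### Adverse-event questions use an undefined floating window and no schedule common to both arms, so counts of minor events may differ through ascertainment

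*Protocol*

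**What the plan says.** **Aim and wording.** Protocol section 9.1.5 states that "Care will be taken not to introduce bias when detecting AEs and/or SAEs". It then offers three open questions. Two of them, on medical problems and on new medicines, run from the last visit or contact; the first of these is "Have you had any (other) medical problems since your last visit/contact". Neither visit nor contact is defined for this purpose.

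**Period and responsibility.** Section 9.1.3 has frequency in its title but gives only the period: "Collection of AEs and SAEs will begin at the time a participant signs informed consent and continues until the follow-up contact". Section 9.1 says that "The Principal Investigator or site staff are responsible for detecting, documenting, and reporting events". Exercise instructors are not mentioned there.

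**Contact in the intervention arm.** Under section 7.1.2, "participants will complete one session per week under the supervision of a physical exercise instructor". Under section 7.1.1, before the home programme starts, "each participant will have a home visit from an exercise instructor". Packages are tailored to the pre-frail domains found at baseline (section 7). Entry requires one or two physical pre-frailty criteria (Table 2), so most or all of this arm are likely to be given the physical package.

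**Contact in the control arm.** Section 7 states that "The no-intervention control arm will not receive any element of the My-AHA intervention". The scheduled post-baseline contacts are the assessments at 6, 12 and 18 months. The exception is a control found to be physically frail at 6 or 12 months, who gains access to the physical package.

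**Questions already common to both arms.** Section 6.4.2 and the follow-up form in Appendix 6 collect falls since the last assessment, diagnoses and current medication from every participant at 6, 12 and 18 months. These items are not named as a source of AEs.

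**The concern.** A window that runs from the last contact is only as long as the gap between contacts, and here that gap depends on the arm. One arm has a supervised weekly class; the other has three scheduled post-baseline contacts in 18 months. Short windows favour recall of minor strains, aches and brief illnesses, and regular contact gives such events more chances to be seen or mentioned. The control is no treatment, so participants know their arm and blinding cannot offset this.

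At stake is the reading of non-serious AEs. If more are recorded in the exercise arm, a true effect of training could not be separated from better capture. Analysis cannot repair this afterwards: the difference arises when the question is put, and section 9 does not ask for the contact at which an event came to light to be recorded.

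**Working it through.** The protocol gives no AE rate, recall rate or calculation for AEs, so there is no figure to reproduce. The contact schedule can be counted; everything after step 1 is illustration on assumed inputs.

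**1. Contacts, from the protocol.** 18 months = 18 × 52/12 = 78 weeks. Intervention arm with the physical package: up to about 78 weekly classes. Control arm: 3 post-baseline assessments, so 78/3 = 26 weeks between them. The possible windows are about 1 week and 26 weeks.

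**2. What the wording implies under each reading.**

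- Questions put at every contact, classes included: windows of about 1 and 26 weeks, with more events likely to be captured in the intervention arm.
- Questions put only at assessments, contact read literally: an intervention participant's last contact may be last week's class, so the question covers about 1 of the 26 weeks (1/26 = 3.8%), while a control's covers all 26. The direction could reverse.
- Questions put only at assessments, contact read as assessment: 26 weeks in both arms and no difference in window. The protocol does not state this rule.

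**3. Size under the first reading (assumed).** Let recall decay exponentially with half-life h weeks. The share captured over a window of T weeks is c(T) = (1 − exp(−kT))/(kT), with k = ln 2/h. With equal true rates, the ratio of reported events (intervention to control) is c(1)/c(26). For h = 13, k = 0.0533, c(1) = 0.974, c(26) = 0.541 and the ratio is 1.80.

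| Half-life (weeks) | c(1) | c(26) | Ratio, weekly | Ratio, monthly |
|---|---|---|---|---|
| 4 | 0.918 | 0.220 | 4.18 | 3.20 |
| 8 | 0.958 | 0.397 | 2.41 | 2.10 |
| 13 | 0.974 | 0.541 | 1.80 | 1.65 |
| 26 | 0.987 | 0.721 | 1.37 | 1.31 |
| 52 | 0.993 | 0.845 | 1.18 | 1.15 |
| 104 | 0.997 | 0.918 | 1.09 | 1.07 |

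The monthly column uses T = 4.33 weeks for the intervention arm. With T = 26 in both arms the ratio is 1.00 at every half-life.

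**4. Effect on the proportion with any AE (assumed rate).** Take 1 true minor AE per person-year in both arms over 1.5 years, with 25 per arm as in section 4. The proportion reporting any AE is 1 − exp(−1.5 × c).

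- h = 13: 1 − exp(−1.5 × 0.974) = 77% against 1 − exp(−1.5 × 0.541) = 56%. A two-sided 5% comparison of proportions would be significant with probability about 35%, although the true rates are equal.
- h = 52: 78% against 72%, with probability about 7%.

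**The case against.** **Weekly questioning is not in the protocol.** A reader might infer that AEs are asked about weekly in one arm and six-monthly in the other, so that unequal recall alone will make the intervention look less safe. The documents do not support this. Section 9.1.5 gives example questions without a schedule, section 9.1 assigns detection to the investigator or site staff, and section 7.1.2 gives class leaders no AE role. Section 6.6.2 uses visit for assessments. This stands: the difference is possible, not established, and its direction depends on how a site reads contact. It does not remove the defect, because the one reading that gives equal windows is not written down.

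**Falls are covered.** A reader might also infer that a benefit on falls could be hidden. Section 6.4.2 and Appendix 6 already ask both arms about falls since the last assessment, so this does not follow.

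**Follow-up is not detection.** Section 9.1.6 says "the investigator is required to proactively follow each participant at subsequent visits/contacts", which may look like more frequent detection. It applies after an event has been reported and is no evidence on how events are first found.

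**No between-arm comparison of AEs is stated.** True; methods of summary commonly belong in the SAP. How and when the question is asked is a matter of data collection, however, and is fixed in the protocol.

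**Unequal contact is inherent.** Any supervised programme set against no treatment has it, and a floating window leaves no period unasked if it is put at every contact. Controls who become frail may also gain class contact, which narrows the gap. These points limit the size; they do not make the windows equal.

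**Conclusion.** The point holds in a limited form. The protocol leaves the AE window undefined and sets no questioning schedule common to both arms, while scheduled contact differs by arm by design. That sits badly with its own aim of avoiding bias in detection. Minor, non-serious AE counts may differ through ascertainment alone, most likely upward in the intervention arm if events surface at classes.

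The size cannot be fixed from the documents. It runs from no effect, if questioning is confined to assessments with a common window, to about fourfold at the shortest assumed half-life with weekly questioning. Those ratios rest on equal true rates, exponential recall decay and class contacts being used for AE questions, none of which the protocol states. Deaths and hospitalisations should depend little on recall.

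**What to change.** In section 9.1.5, ask both arms the same scripted AE questions at 6, 12 and 18 months, with the window set to the time since the last scheduled assessment. Section 6.4.2 and Appendix 6 already use that kind of anchor. Base any between-arm comparison of AEs on those answers.

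Continue to record and report, for safety, events noted at classes, home visits or other contacts. Flag them by source and list them separately.

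The cost is about two sentences and one source field on the AE form. The downside is that the compared counts will miss some minor events in both arms, because six-month recall is incomplete; equal windows give up some sensitivity for comparability.
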